9.7. Dose Reduction/Interruption/Delay

Dose reduction/interruption/delay will be summarized separately for each drug. The number of subjects who have at least one dose reduction/interruption/delay, number of dose reductions/interruptions/delays per subject, and reason for dose reduction/interruption/delay will be summarized.

10. EFFICACY ANALYSIS

Primary efficacy analyses will be performed on the FAS population. Supportive efficacy analyses will also be performed using the EE Population.

All analyses will use descriptive statistics.

Tumor response, including PD, will be assessed by the investigators and the IRAC using the International Myeloma Working Group (IMWG) uniform response criteria.

10.1. Overall Response Rate

The primary efficacy endpoint will be based on tumor responses as assessed by an IRAC using the IMWG Uniform Response Criteria. The ORR will be calculated as the number of responders (PR or better), divided by the number of subjects in the FAS population. The ORR together with the proportions in each category based on the IMWG criteria (ie, stringent complete response [sCR], complete response [CR], very good partial response [VGPR], PR, stable disease [SD], and PD. Refer [Table 6](#)) will be tabulated, together with the 2-sided exact 95% CI.

Listings of lab assessments for efficacy parameters will also be provided.

10.2. Time to Response

The time to response (TTR) (for responders only, per IMWG uniform response criteria) is calculated as the time from treatment initiation of the study treatment to the first date of documented response (PR or better). Time to response will be summarized using descriptive statistics.

10.3. Duration of Response

Duration of response (DOR; for responders only, per IMWG Uniform Response Criteria) is defined as the time from the earliest date of documented response (PR or better) to the first documentation of PD or death, whichever is earlier. Duration of response will be analyzed using the KM method. Median DOR along with the two-sided CI will be provided. Censoring for DOR will follow the same rules for Progression-free survival (see [Table 5](#)).

10.4. Progression-free survival

Progression-free survival (PFS) is defined as the time from treatment initiation to the first date of documented PD or death from any cause during the study whichever occurs earlier.

Subjects who do not have a PFS event will be censored on the last adequate assessment date. Progression-free survival will be summarized for the FAS using Kaplan-Meier (KM) statistics.

Subjects who had PD prior to receiving other antimyeloma therapy will be considered to have the event on the date of PD. Subjects who died without documented PD and without receiving other antimyeloma therapy will be considered to have an event on the date of death. Subjects who did not have disease progression at the time of the data cut-off date will be censored on the date of their last adequate response assessment on or prior to the cut-off date. For subjects with PD documented between scheduled assessments, the event will be considered to have occurred

on the date of last scheduled adequate assessments with no progression. The censoring rules for PFS are provided in [Table 5](#). These rules are based on the United States Food and Drug Administration (US FDA) guidance for cancer trial endpoints ([FDA Guidance, 2007](#)).

Table 5: Censoring Rules for Progression-free Survival

Situation	Date of Progression or Censoring	Situation Outcome
Death within the first two scheduled assessments without disease progression	Date of death	Event
Progression	If the first PD is a scheduled assessment, then Date of first PD; If the first PD is an unscheduled assessment and no previous assessment, then Date of PD; If the first PD is an unscheduled assessment and has previous assessment, then Date of previous assessment (regardless of the response type)	Event
Death between scheduled assessments	Date of death	Event
No progression	Date of last adequate assessment with evidence of no progression	Censored
Death or progression after two or more missed scheduled assessments	Date of last adequate assessment with evidence of no progression	Censored
New antimyeloma / non-protocol cancer treatment started prior to progression or death due to any reason	Date of last adequate assessment with evidence of no progression before the start of new treatment	Censored

PD = progressive disease.

Source: United States Food and Drug Administration (US FDA) guidance for cancer trial endpoints for the approval of cancer drugs and biologics ([FDA Guidance, 2007](#)).

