## 9.6.2. Secondary Efficacy Endpoints

Time-to-response (for responders only, per IMWG Uniform Response Criteria) is calculated as the time from treatment initiation of study treatment to the first date of documented response (PR or better). Time to response will be summarized using descriptive statistics.

Duration of response (for responders only, per IMWG criteria) is defined as time from the earliest date of documented response (PR or better) to the first documentation of PD or death, whichever is earlier. Duration of response will be analyzed using the Kaplan-Meier (KM) method. Median duration of response along with the two-sided CI will be provided.

Progression-free survival is defined as time from treatment initiation to the first date of documented PD or death from any cause during the study, whichever occurs earlier. Subjects who do not have a PFS event will be censored on the last adequate assessment date. PFS will be summarized using the KM method.

Overall survival is defined **as** time from treatment initiation to death due to any cause. Subjects who are alive or lost to follow-up will be censored on the last-known-alive date. The OS will be analyzed using the KM method. Median OS and the corresponding 95% CI will be provided.

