4. INVESTIGATIONAL PLAN

4.1. Overall Study Design and Plan

This is a single-arm, multicenter, Phase 2 study to evaluate the efficacy and safety of the combination regimen of D². The study will consist of 2 parts; Part 1 has a 2-stage design while Part 2 consists of an expansion phase (see [Figure 1](#)) Subjects will receive intravenous (IV) DARA at 16 mg/kg on the same dosing schedule (weekly [QW], every 2 weeks [Q2W] or every 4 weeks [Q4W] of each 28-day cycle) received on their last prior therapy containing DARA. The dosing schedule for DARA may be adjusted during the course of the study. Subjects will also receive IV DURVA at 1500 mg on Day 2 (Cycle 1) and on Day 1 (Cycles \geq 2) of each 28-day treatment cycle. The dosing schedule is outlined in [Table 2](#).

Figure 1: Overall Study Design

D² = daratumumab + durvalumab; ORR = Overall Response Rate; PD = Progressive Disease

Table 2: Dosing Schedules

IV DURVA (Dose: 1500 mg)	IV DARA (Dose: 16 mg/kg)
Cycle 1: Day 2 / 28-day cycle	Subjects should start study treatment on the same dosing schedule as their last DARA-containing regimen (QW, Q2W, or Q4W)
Cycle \geq 2: Day 1 / 28-day cycle	
The dosing schedule should be modified, during the course of the study, as shown below, provided that the subject has a response of stable disease (SD) or better:
 
QW frequency (Days 1, 8, 15, and 22/ 28-day cycle): Weeks 1 to 8, then Q2W from Weeks 9 to 24, then Q4W from Weeks 25 and onward
 
Q2W frequency (Days 1, 15/ 28-day cycle): Weeks 1 to 16, then Q4W from Weeks 17 and onward
 
Q4W frequency (Day 1/28-day cycle): Week 1 onwards until disease progression

DARA = daratumumab; DURVA = durvalumab; IV = intravenously; QW = weekly; Q2W = every 2 weeks; Q4W = every 4 weeks.

An Independent Response Adjudication Committee (IRAC) will be set up for this trial to review study data. The IRAC will determine tumor response to therapy and will confirm the time of progressive disease (PD) (if disease progressed) at scheduled or unscheduled visits for each subject.

The safety and efficacy of the study will be monitored by an independent Data Monitoring Committee (DMC) who is not involved in the trial conduct. The DMC will meet and review study data at pre-specified intervals throughout the trial.

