13. INTERIM ANALYSIS

This study will be conducted in 2 parts with two interim analyses being planned.

The first interim analysis will be conducted at the end of Stage 1 of Part 1, when the first 18 subjects enrolled have completed at least 3 cycles of treatment. If at least 3 subjects out of 18 achieve a response (PR or better), the study will continue to Stage 2. The second interim analysis will be conducted at the end of Stage 2. If at least 9 subjects achieve a response (PR or better) out of a total of 50 subjects and it is determined by the Sponsor to further confirm the efficacy and safety of D², an additional 70 subjects may be enrolled.

CELGENE PROPRIETARY INFORMATION

**14. CHANGES TO THE STATISTICAL ANALYSES SECTION OF
THE PROTOCOL**

Not applicable.

CELGENE PROPRIETARY INFORMATION

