16. APPENDICES

16.1. Handling of Dates

Dates will be stored as numeric variables in the SAS analysis files and reported in DDMMYY format (ie, the Date9. datetime format in SAS). Dates in the clinical database are classified into the categories of procedure dates, log dates, milestone dates, outcome dates, and special dates.

- **Procedure Dates** are the dates on which given protocol-specified procedure are performed. They include the dates of laboratory testing, physical examinations, tumor scans, etc. They should be present whenever data for a protocol-specified procedure are present and should only be missing when a procedure are marked as NOT DONE in the database. Procedure dates will not be imputed.
- **Log Dates** are dates recorded in CRF data logs. Specifically, they are the start and end dates for adverse events and concomitant medications/procedures. They should not be missing unless an event or medication is marked as *ongoing* in the database. Otherwise, incomplete log dates will be imputed according to the rules in Appendix 16.2 (eg, for duration or cycle assignment, etc). However, in listings, log dates will be shown as recorded without imputation.
- **Milestone Dates** are dates of protocol milestones such as randomization, study drug start date, study drug termination date, study closure date, etc. They should not be missing if the milestone occurs for a subject. They will not be imputed.
- **Outcome Dates** are dates corresponding to study endpoints such as survival, progression, etc. In most cases they are derived either from a milestone (eg, the survival date is derived from the death date), or a procedure date (eg, the progression date is derived from the date of the tumor scan that was used to determine progression). They may be subject to endpoint-specific censoring rules if the outcome did not occur, but are not otherwise subject to imputation.
- **Special Dates** cannot be classified in any of the above categories and they include the date of birth. They may be subject to variable-specific censoring and imputation rules.

Dates recorded in comment fields will not be imputed or reported in any specific format.

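### SAP 10.4 back-dates an unscheduled progression by two different rules, and neither gives the documented PD date that the protocol and the SAP's own definition require

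*SAP*

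**What the plan says.** The definition in SAP 10.4 reads "Progression-free survival (PFS) is defined as the time from treatment initiation to the first date of documented PD or death from any cause". Protocol 9.6.2 matches it: "Progression-free survival is defined as time from treatment initiation to the first date of documented PD or death from any cause during the study". The protocol has a censoring sentence for subjects without an event but no rule that moves a PD date.

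SAP 10.4 then gives two rules for a PD that does not fall on a scheduled visit. The running text places the event "on the date of last scheduled adequate assessments with no progression". The Progression row of Table 5 says "If the first PD is an unscheduled assessment and has previous assessment, then Date of previous assessment (regardless of the response type", and uses the PD date itself when there is no previous assessment.

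Other sections bear on the same date:

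- SAP 16.1 gives the usual source of an outcome date, with this example: "the progression date is derived from the date of the tumor scan that was used to determine progression". It adds: "They may be subject to endpoint-specific censoring rules if the outcome did not occur, but are not otherwise subject to imputation".
- SAP 4.1 says the IRAC "will confirm the time of progressive disease (PD) (if disease progressed) at scheduled or unscheduled visits for each subject".
- SAP 10.3 and 10.5 refer DOR and TTP to Table 5.
- SAP Section 14, which should list changes to the protocol's statistical section, says "Not applicable".

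**The concern.** Two programmers could each follow SAP 10.4 faithfully and deliver different PFS datasets. The text requires the substituted assessment to be scheduled, adequate and free of progression. Table 5 requires only that it came before. A plan meant to fix the analysis before database lock should not leave the event date to whoever codes it.

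Separately, either rule replaces the documented PD date with an earlier one. That departs from the protocol's definition and from the SAP's own, and Section 14 does not declare it. What is at stake is the reproducibility of the secondary time-to-event results and their traceability to the protocol. No bias relative to the true progression time is claimed.

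**Working it through.** **Step 1: the rules side by side.**

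| Source | Event date for an unscheduled PD |
|---|---|
| SAP 10.4 definition; Protocol 9.6.2 | Date PD is first documented |
| SAP 10.4 text | Last scheduled, adequate, progression-free assessment |
| SAP Table 5, previous assessment exists | Previous assessment of any kind |
| SAP Table 5, no previous assessment | Date of PD |
| SAP 16.1 | Usually the determining scan; no imputation once the outcome has occurred |

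**Step 2: worked dates.** Protocol 6.4.5.1 has response assessed on Day 1 of each 28-day cycle from Cycle 2, so the nominal visits are Days 29, 57 and 85. SAP 16.1.1 converts days to months by dividing by 30.4167: 80 → 2.63, 75 → 2.47, 57 → 1.87, 29 → 0.95.

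| Case | Definition | Text | Table 5 |
|---|---|---|---|
| A. Scheduled Days 29 and 57 adequate, unscheduled SD Day 75, unscheduled PD Day 80 | Day 80 (2.63) | Day 57 (1.87) | Day 75 (2.47) |
| B. Adequate SD Day 29, Day 57 not evaluable, unscheduled PD Day 80 | Day 80 (2.63) | Day 29 (0.95) | Day 57 (1.87) |
| C. Unscheduled PD Day 20, no earlier response assessment | Day 20 | Not defined | Day 20 |
| D. Scheduled SD Day 57, unscheduled PD Day 75, nothing between | Day 75 (2.47) | Day 57 (1.87) | Day 57 (1.87) |

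Text and table differ by 75 − 57 = 18 days in A and 57 − 29 = 28 days in B. They agree in D, the simple case. Case B assumes that a not-evaluable visit counts as a previous assessment, which Table 5 does not settle.

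**Step 3: range on the nominal schedule.** Put the last scheduled visit at day 0 and the next at day 28, with an unscheduled non-PD assessment on day a and an unscheduled PD on day b, 1 ≤ a < b ≤ 27. There are 27 × 26 / 2 = 351 pairs.

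- Text versus table: a, from 1 to 26 days.
- Table versus documented date: b − a, from 1 to 26 days.
- Text versus documented date: b, from 2 to 27 days.

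With no intermediate assessment, both rules move the event back by b, from 1 to 27 days. These ranges assume adequate scheduled visits. In case B the text rule moves the event 80 − 29 = 51 days. The ±3-day visit window would also let some late days count as the scheduled visit.

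**Step 4: effect of back-dating on the median.** The documents give neither the PFS distribution nor the share u of PDs found at unscheduled visits, so both are assumptions. The model uses exponential PD times with medians of 2, 3 and 4 months and no censoring. A share u is documented on the true day and the rest at the next scheduled visit. The back-dated event takes the previous post-baseline scheduled visit, or the PD date if there is none. There were 8,000 trials at each of n = 18, 50 and 120. Text and Table 5 coincide in this model, so it measures back-dating, not the conflict between them.

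| u | Mean fall in median (months) | Trials with no shift, two middle times averaged | Trials with no shift, lower middle time |
|---|---|---|---|
| 10% | 0.04–0.05 | 82–85% | about 88–92% |
| 20% | 0.08–0.11 | 67–74% | about 77–83% |
| 40% | 0.15–0.20 | 40–54% | about 54–65% |

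Events that move do so by 13.3 to 13.6 days on average.

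On a 28-day grid the median tends either to stay put or to jump. A large-sample run under separate assumptions (medians of 2, 4 and 6 months; u of 10%, 25% and 50%) left it unchanged in most scenarios. The largest fall was from 2.57 to 1.87 months, or 0.70, at a median of 2 months and u = 25%.

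**Step 5: accuracy.** With an underlying median of 3 months and u = 40%, mean times are 4.34 months (true), 4.48 (back-dated) and 4.62 (documented). The documented date lies further from the truth in this model, so the case for it is consistency with the protocol, not accuracy.

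**The case against.** The strongest reply is that this is one sentence to harmonise, not a contradiction across the plan.

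- The Table 5 row concerns the first PD, so the previous assessment can hardly be a PD, and its wording on response type probably means any category from sCR to SD. This stands: in practice the rules part only when the preceding assessment is unscheduled or inadequate, or does not exist.
- SAP 16.1 says its source rule holds in most cases, and elsewhere in Section 16 imputation means completing partial dates. This weakens the 16.1 point but does not remove it: the clause barring other imputation carries no such qualifier, and it allows endpoint-specific rules only when the outcome did not occur.
- The IRAC confirms a time of PD; nothing says the analysis must use it unaltered. That is fair as far as SAP 4.1 goes, though Protocol 6.4.5.2 does say that adjudicated response data feed every efficacy analysis.
- A SAP may elaborate on a one-line protocol definition, and whether back-dating belongs in Section 14 is partly judgement. But replacing the documented date changes what the definition says, which is more than added detail.
- SAP 10.3 carries over censoring, while the disputed row is an event row, so the effect on DOR is an inference. It is supported by SAP 10.5, which treats the death-event rows as part of the censoring rules. SAP Table 3 bases DOR on investigator assessment, so the IRAC argument does not reach DOR there.
- Back-dating can only shorten PFS, so it cannot flatter the treatment, and Table 5 cites a regulatory guidance that was not available here. Neither point tells a programmer which of the two rules to apply.

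**Conclusion.** The concern holds. SAP 10.4 does not give a single event date for an unscheduled PD, and both back-dating rules depart, undeclared, from the definition in Protocol 9.6.2 and in SAP 10.4 itself. The text–table conflict is certain from the wording. The conflict with SAP 16.1 and the omission from Section 14 are well supported but involve some interpretation.

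The size is modest. Where one unscheduled non-PD assessment intervenes, text and table differ by 1 to 26 days on the nominal schedule, or by a full 28-day interval if the preceding scheduled visit was inadequate. How often this would happen cannot be estimated from the documents. The median-PFS results rest on assumed shares of unscheduled PD; averaged over trials the fall was at most 0.20 months, although a jump of about 0.7 month is possible in an unfavourable configuration.

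The affected endpoints are secondary and descriptive. ORR and the 3-of-18 and 9-of-50 rules count responders and do not use this date. The point should be fixed before the SAP is finalised, but it does not threaten the primary conclusion.

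**What to change.** State one event date, in identical words, in the 10.4 text and in the Progression row of Table 5: the event falls on the date of the first assessment, scheduled or unscheduled, that documents PD. Say in 10.3 and 10.5 that the same date applies to DOR and TTP. Any back-dating rule can be kept as a named sensitivity analysis with a single definition.

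If the sponsor prefers back-dating as the main analysis, that is workable provided that:

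- one rule appears in both the text and the table, covering the case of no previous assessment and stating whether a not-evaluable visit and the EOT visit count;
- 16.1 is amended to allow it;
- Section 14 lists the departure from Protocol 9.6.2.

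The cost is a few lines of SAP wording in 10.3 to 10.5 and Table 5, plus 16.1 and Section 14 only under the second option, and a few lines of programming. No new data are needed.

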10.5. Time to Progression

Time to progression (TTP) is defined as time from treatment initiation to the first documented progression, confirmed by IRAC. Censoring rules for TTP are similar as for PFS (see [Table 5](#)), however Death within the first two scheduled assessments without disease progression and Death between scheduled assessments will be censored at the date of death. The TTP will be analyzed using the KM method. Median TTP and the corresponding 95% CI will be provided.

10.6. Overall Survival

Overall survival (OS) is defined as time from treatment initiation to death due to any cause. Subjects who died will be considered as having events on the date of death. Subjects who are

alive or lost to follow-up will be censored on the last-known-alive date. The OS will be analyzed using the KM method. Median OS and the corresponding 95% CI will be provided.

CELGENE PROPRIETARY INFORMATION

11. SAFETY ANALYSIS

The purpose of this section is to define the safety parameters for the study. The safety variables for this study include AEs, clinical laboratory evaluations, 12-lead ECGs, physical examinations, vital signs, pregnancy testing for females of childbearing potential and concomitant medications and procedures. All summaries of safety data will be conducted using the Safety Population unless otherwise specified.

Individual subject listings will be provided for the FAS to support the tables.

11.1. Adverse Events

Adverse events will be analyzed in terms of treatment-emergent AEs (TEAEs) which are defined as any AEs that begin or worsen on or after the start of study drug through 90 days after the last dose of DURVA or DARA, whichever is later. All AEs will be coded using the MedDRA Version 19.0 or higher.

A treatment-related TEAE is defined as a TEAE which is considered to be related to the study drug.

If a subject experiences the same AE more than once with different toxicity grade, then the event with the highest grade will be tabulated in “by grade” tables. If a subject experiences multiple AEs under the same PT (SOC), then the subject will be counted only once for that PT (SOC). In addition, AEs with a missing intensity will be presented in the summary table as an intensity category of “Missing.”

The incidence of TEAEs will be summarized by MedDRA SOC and PT. The intensity of AEs will be graded 1 to 5 according to the National Cancer Institute Common Terminology Criteria for Adverse Events (NCI CTCAE) Version 4.03 or higher. For all other AEs not described in the CTCAE criteria, the intensity will be assessed by the investigator as mild (Grade 1), moderate (Grade 2), severe (Grade 3), life-threatening (Grade 4) or death (Grade 5). Tables summarizing the incidence of TEAEs will be generated for each of the following:

- All TEAEs;
- All TEAEs by decreasing frequency of PT
- TEAEs by cycle;
- TEAEs for the first cycle;
- All TEAE with NCI CTCAE Grade 1-2;
- All TEAE with NCI CTCAE Grade 3-4;
- All TEAE with NCI CTCAE Grade 5;
- TEAEs reported as treatment-related;
- Treatment-related TEAEs with NCI CTCAE Grade 1-2;
- Treatment-related TEAEs with NCI CTCAE Grade 3-4;
- Treatment-related TEAEs with NCI CTCAE Grade 5;

- Serious TEAE;
- Treatment-related serious TEAEs;
- TEAEs leading to permanent discontinuation of study drug;
- Treatment-related TEAEs leading to permanent discontinuation of study drug;
- TEAEs leading to study drug dose delay/interruption/infusion interruption;
- TEAEs leading to death;
- Overall deaths;
- Deaths within 28/60/90 days of the last dose of study drug;
- Deaths within first 60 days from Cycle 1 Day 1.

Listings for the corresponding summary tables will be presented separately. A listing for non-treatment-emergent AEs will also be provided.

